### 9.4. Total Bile Acids, Total Endogenous Bile Acids, C4 and FGF-19 Concentrations

Total bile acids, total endogenous bile acids, C4 and FGF-19 concentrations will be analyzed as follows:

- Summary statistics of total bile acids, total endogenous bile acids, C4 and FGF-19 concentrations including baseline values, change from baseline, and percentage change from baseline values will be presented by treatment group and by each scheduled post-baseline visit.

- Change from baseline in total bile acids, total endogenous bile acids, C4 and FGF-19 concentrations at each scheduled post-baseline visit will be analyzed using the Wilcoxon Rank Sum Test.

### 9.5. Noninvasive Measurements of Liver Stiffness and Fibrosis

Noninvasive measurements of liver stiffness (TE) and liver fibrosis (ELF [HA, P3NP, and TIMP-1]) will be analyzed as follows:

- Summary statistics of TE and ELF including baseline values, change from baseline, and percentage change from baseline values will be provided by treatment group and by each scheduled post-baseline visit.
- Analyses of change from baseline in liver stiffness and liver fibrosis values will be analyzed by using an ANCOVA model with change from baseline as the dependent variable, treatment group and randomization stratification factor as fixed effects and the baseline value as a covariate.
- Analyses of percent change from baseline in liver stiffness and liver fibrosis values will be analyzed by using an ANCOVA model with percent change from baseline as the dependent variable, treatment group and randomization stratification factor as fixed effects and the baseline value as a covariate.

As a sensitivity analysis, change from baseline and percent change from baseline of these parameters will be analyzed using the same MMRM model as described in [Section 9.3](#).

### 9.6. Clinical Outcome Events

The following clinical outcome events will be captured in the study:

- Time from first dose to death (all cause)
- Time from first dose to liver-related death
- Time from first dose to liver transplant
- Time from first dose to MELD score  $\geq 15$  (for patients with MELD  $\leq 12$  at baseline)
- Time from first dose to earliest hospitalization for new onset or recurrence of:
  - variceal bleed
  - hepatic encephalopathy (as defined by a West Haven score of  $\geq 2$ )
  - spontaneous bacterial peritonitis (confirmed by diagnostic paracentesis)
- Time from first dose to uncontrolled ascites (diuretic resistant ascites requiring therapeutic paracentesis at a frequency of at least twice in a month)
- Time to first occurrence of any above listed clinical events

The incidence and time to first occurrence of any above listed clinical events will be summarized by treatment group using the log rank test stratified by the randomization stratification factor. The minimum and maximum time to clinical event will be presented. KM estimates of the

distribution of the time-to-event will be tabulated and graphed by treatment group. The tabulation will include the KM methodology using 25th, 50th (median), and 75th percentiles with associated 2-sided 95% CIs, as well as percentage of censored observations. The number and percent of patients censored and with events will be presented. The hazard ratio and 2-sided 95% CI will be estimated based on a Cox regression model stratified by randomization strata. The proportionality of hazards will be assessed using Schoenfeld residuals.

In addition, the incidence and time to each of the above clinical events, and the incidence and time to occurrence of HCC will be summarized by treatment group using the same methods as defined above.

For the time to event analyses, subjects who do not experience an event will be censored at the time of their last contact. Subjects with no data after randomization will be considered to have an event on Day 1 (first day of IP dosing). All time-to-event endpoints include only adjudicated events.

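### Section 9.6 uses Kaplan-Meier for individual clinical events without treating death as a competing risk, so the component curves overstate event probability

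*SAP*

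**What the plan says.** Section 9.6 of the SAP lists the clinical outcome events separately. All-cause death and transplant are endpoints in their own right ("Time from first dose to liver transplant"), and the list ends with a composite, "Time to first occurrence of any above listed clinical events".

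For the composite the estimator is KM, shown both as a table and as a curve ("distribution of the time-to-event will be tabulated and graphed by treatment group"), and quartiles with confidence intervals are required. The same section adds a stratified log-rank test and a Cox model: "The hazard ratio and 2-sided 95% CI will be estimated based on a Cox regression model stratified by randomization strata".

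The individual events come next. Their scope is given as "In addition, the incidence and time to each of the above clinical events, and the incidence and time to occurrence of HCC". No separate approach is set for them; the sentence closes by carrying over the composite's, so that they "will be summarized by treatment group using the same methods as defined above".

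One censoring rule covers every time-to-event analysis in the section: "subjects who do not experience an event will be censored at the time of their last contact". Appendix A (General Methods) also names KM as the convention for time-to-event data. Nowhere does the SAP call death or transplant a competing event, ask for a cumulative incidence function, or say when time at risk ends for a transplanted patient.

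**The concern.** KM gives an event probability only if a censored patient could still have the event later. That is reasonable for a patient who is alive when follow-up ends. It fails for a patient who has died. Censoring at death is not spelled out in the SAP, but it follows from the last-contact rule, because a patient who dies without the component event has no contact after death. The estimator then redistributes that patient's probability to those still at risk, and 1−KM answers what would happen if nobody died first.

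The patients have Child-Pugh B or C disease, with at least 20% in class C (section 3), and the SAP itself lists death as an outcome. If deaths differ between arms, the component curves are inflated by different amounts, so a visual comparison can mislead even where the hazard ratio does not. With no formal hypothesis (section 2.2), the descriptive curves and quartiles are a main product of section 9.6.

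**Working it through.** The SAP states no event rate, event count or power for these endpoints, so there is no figure of its own to reproduce. The check takes the rules as written and uses assumed rates to show size.

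**Inputs from the SAP.** KM with last-contact censoring for each component (section 9.6). At least 48 weeks of treatment, continuing to approximately 3 years (section 3). About 50 patients, 1:1, so 50/2 = 25 per arm (section 3.3).

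**Assumptions.** Constant hazards: component a = 0.20 per year; death without the component d = 0.05 to 0.30 per year. 48 weeks = 48/52.18 = 0.92 years.

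**Step 1: death only.**
- With death censored: 1−KM = 1 − exp(−a·t)
- True probability: CIF = a/(a+d) × [1 − exp(−(a+d)·t)]

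At 3 years, 1−KM = 1 − exp(−0.60) = 45.1% whatever d is.

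| d per year | CIF at 3 years | Overstatement, points |
|---|---|---|
| 0.05 | 0.80 × (1 − e^−0.75) = 42.2% | 2.9 |
| 0.10 | 0.667 × (1 − e^−0.90) = 39.6% | 5.6 |
| 0.20 | 0.50 × (1 − e^−1.20) = 34.9% | 10.2 |
| 0.30 | 0.40 × (1 − e^−1.50) = 31.1% | 14.0 |

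At 48 weeks, 1−KM = 1 − exp(−0.184) = 16.8%, against a CIF of 16.4% (d = 0.05) to 14.7% (d = 0.30). The gap is 0.4 to 2.1 points.

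With a = 0.10 per year the 3-year figures are 25.9% against 24.2% to 17.5%.

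**Step 2: effect on a tabulated quartile.** The KM 25th percentile is −ln(0.75)/0.20 = 1.44 years. The time at which the CIF reaches 25% is −ln[1 − 0.25(a+d)/a]/(a+d). For d = 0.05 this is −ln(0.6875)/0.25 = 1.50 years; for d = 0.30 it is −ln(0.375)/0.50 = 1.96 years.

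**Step 3: transplant under the last-contact rule.** A transplant is not itself a censoring time. If follow-up continues, the patient remains in the denominator. Take transplant at rate τ, with no component events and no deaths after transplant (assumptions). Write k = τ/(a+d+τ) and P = exp(−(a+d+τ)·t). The cumulative hazard that KM sees is

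[a/(a+d+τ)] × [1/(1−k)] × (−ln[k + (1−k)P]).

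- a = 0.20, d = 0, τ = 0.20, 3 years: k = 0.5, P = e^−1.2 = 0.301, cumulative hazard 0.430, 1−KM = 34.9%. The CIF is 0.50 × (1 − 0.301) = 34.9%, so there is no overstatement. Censoring at transplant would have given 45.1%.
- a = 0.20, d = 0.10, τ = 0.10, 3 years: k = 0.25, cumulative hazard 0.495, 1−KM = 39.0%. The CIF is 34.9%, and censoring both would give 45.1%.

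The overstatement therefore comes from death. Transplanted patients left at risk dilute the component hazard when events are rarer after transplant.

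**The case against.** The case for leaving the plan alone has real weight.

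- The events are exploratory (section 2.1.3) and nothing is formally tested. With 25 per arm and a probability near 40%, the 95% half-width is about 1.96 × √(0.24/25) = 19 points before any censoring, more than any bias shown above. This stands and limits severity. It does not make a systematic error harmless, since the remedy needs no data.
- The composite includes death and transplant, all-cause death has no competing death, and numbers and percentages with events are tabulated as well. This stands. Those outputs need no change.
- Section 9.6 asks for curves and quartiles, not fixed-time percentages. Also true; the 45% is a point on a curve, not a named table entry. The quartiles shift too.
- Three years is the longest follow-up. Late entrants have less, and at 48 weeks the gap is about 0.4 to 2 points. This stands.

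A reader might infer that transplant is censored like loss to follow-up. The text does not say so: censoring is at last contact. The two coincide only if follow-up ends at transplant, which the SAP does not state and the protocol, not at hand, may settle. A reader might also infer that transplant makes every listed event impossible. It does not: liver-related death can follow a transplant, MELD is computed from bilirubin, creatinine and INR (section 9.1), and section 9.6 does not restrict events to the native liver. Whether later events count is a choice the SAP should state.

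**Conclusion.** The point holds for the KM curves and quartiles of liver-related death, transplant, MELD ≥15, hospitalization, uncontrolled ascites and HCC. Wherever patients die first, censoring those deaths makes 1−KM too high. Under the assumed constant hazards the excess is about 3 to 14 points at 3 years and 0.4 to 2.1 points at 48 weeks for a component at 0.20 per year. These are illustrations, not predictions, because the SAP supplies no rates.

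It would be tempting to read the table's d as death and transplant combined. That reading is right only if follow-up stops at transplant. If it continues, the excess shrinks (39.0% against 34.9% with each at 0.10 per year) and vanishes in the example with transplant alone.

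Nor does the point discredit the log-rank test or the Cox model: with death censored, both compare cause-specific hazards. Severity is low to moderate.

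**What to change.** In section 9.6, replace KM by the Aalen-Johansen cumulative incidence function for the six components, and name the competing events:

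- **MELD ≥15, hospitalization, uncontrolled ascites, HCC:** death and transplant compete. This also fixes the end of time at risk at transplant.
- **Transplant:** death competes.
- **Liver-related death:** only non-liver-related death competes. Deaths after transplant are kept.

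Keep KM for all-cause death and the composite. Keep the stratified log-rank and Cox results for the components and label them cause-specific. Make the matching exception in Appendix A, General Methods.

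The cost is SAP wording and a standard software option, with no new data or patients. The downside is that quartiles may not be reached. With d = 0.30 in the illustration, the cumulative incidence can never exceed 0.20/0.50 = 40%, so no median would exist.

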### **3.3. Sample Size Determination**

To reasonably characterize the PK of OCA in patients with hepatic impairment, a simulation-based approach estimated a requirement of approximately 20 patients in the OCA treatment group assuming a 15% discontinuation rate. A total of 30 patients is adequate with 10 patients on placebo to be included as a comparator and 20 patients on OCA. An additional 20 patients will be enrolled to support safety and efficacy evaluations. Therefore, approximately 50 patients (including at least 20% of patients with CP-C) will be randomized in a 1:1 ratio to 1 of 2 treatment groups: placebo and OCA.

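### SAP Section 9.6 plans an ordinary stratified Cox hazard ratio for each single clinical event and HCC, with about 25 patients per arm and no rule for an arm without events

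*SAP*

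**What the plan says.** For the first occurrence of any listed clinical event, SAP Section 9.6 plans a stratified log-rank test, Kaplan-Meier estimates, a hazard ratio and a check of proportional hazards by Schoenfeld residuals. On the hazard ratio it says: "The hazard ratio and 2-sided 95% CI will be estimated based on a Cox regression model stratified by randomization strata".

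It then carries these methods over to the components. "In addition, the incidence and time to each of the above clinical events, and the incidence and time to occurrence of HCC" are to be summarized in the same way. That gives seven single endpoints: all-cause death, liver-related death, transplant, MELD of 15 or more (only in patients with baseline MELD of 12 or less), first qualifying hospitalization, uncontrolled ascites and HCC. If the three causes of hospitalization are analysed separately, there are nine.

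Section 9.6 sets no minimum number of events, names no penalized or exact method, does not say how the confidence limits are formed, and has no rule for an arm without events.

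On size, Section 3.3 says "approximately 50 patients (including at least 20% of patients with CP-C) will be randomized in a 1:1 ratio". The number was built from pharmacokinetics ("A total of 30 patients is adequate with 10 patients on placebo to be included as a comparator and 20 patients on OCA") and then enlarged: "An additional 20 patients will be enrolled to support safety and efficacy evaluations". No event rate, event count or power is given for any clinical outcome.

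**The concern.** If all events of one type fall in one arm, the Cox partial likelihood keeps rising as the log hazard ratio moves towards plus or minus infinity, so it has no finite maximum. The printed estimate then depends on where the software stops iterating. Wald limits, the usual default, run from about 0 to infinity. If neither arm has an event there is nothing to estimate. A Schoenfeld check on a handful of events tells the reader nothing in any case.

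A one-sided count, such as 0 against 3 transplants, is a pattern a safety reader would want summarized well, and it is where the planned estimate and a Wald interval say nothing. Section 9.3 foresees model failure for the MMRM: it gives a sequence of covariance structures and says that nothing is reported if the last one fails. Section 9.6 has no counterpart. The decision to print, suppress or replace a degenerate hazard ratio would therefore be taken after the data are seen.

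**Working it through.** **Inputs from the SAP.** Section 3.3: 20 OCA and 10 placebo patients for pharmacokinetics, 20 more for safety and efficacy, 1:1 allocation, at least 20% CP-C.

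**The plan's own figure.** 20 + 10 + 20 = 50, and 50/2 = 25 per arm, so the stated total reproduces. CP-C: 0.20 × 50 = 10 patients, about 5 per arm.

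**Assumed.** The cumulative risk p of a given component over follow-up, equal in both arms. The SAP gives no value, so a range is shown. The calculation ignores the Section 9.6 rule that counts a patient with no data after randomization as an event on Day 1.

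**Step 1: chance of no finite hazard ratio for one component.** Let q = (1 − p)^25 be the chance that an arm has no event. Then P(both arms empty) = q², P(exactly one empty) = 2q(1 − q), and P(no finite hazard ratio) = 1 − (1 − q)². For p = 5%: q = 0.95^25 = 0.277, and 1 − 0.723² = 0.478.

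| p | Expected events per arm | Both empty | Exactly one empty | No finite HR |
|---|---|---|---|---|
| 2% | 0.5 | 36.4% | 47.9% | 84% |
| 5% | 1.25 | 7.7% | 40.1% | 48% |
| 8% | 2.0 | 1.5% | 21.8% | 23% |
| 10% | 2.5 | 0.5% | 13.3% | 14% |
| 20% | 5.0 | 0.0% | 0.8% | 0.8% |

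A simulation of the stratified model (20 + 20 CP-B, 5 + 5 CP-C) agreed with the formula: a finite hazard ratio arose in 16%, 41%, 77%, 92% and 99% of trials at risks of 2%, 4%, 8%, 12% and 20%.

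**Step 2: the same question given the total number of events d.** No value of p is needed here, only equal risk. P(all in one arm) = 2·C(25,d)/C(50,d).

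- d = 1: 100%
- d = 2: 2 × 300/1,225 = 49%
- d = 3: 2 × 2,300/19,600 = 24% (23.5%)
- d = 4: 2 × 12,650/230,300 = 11%
- d = 5: 2 × 53,130/2,118,760 = 5%

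**Step 3: the restricted endpoint.** The size of the subset with baseline MELD of 12 or less is not stated. If it were 12 per arm (assumed), q = 0.9^12 = 0.282 at 10% risk and P(no finite HR) = 1 − 0.718² = 49%. At 20% risk it is 13%.

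**Step 4: what the two methods return for 0 against 3 events, 25 per arm.** An ordinary Cox fit did not converge; it gave a hazard ratio of about 2 × 10^12 with limits 0 to infinity. With Firth's penalty the log hazard ratio is 1.99, so HR = e^1.99 = 7.3, with profile-likelihood 95% limits of 0.7 to about 980. Stratifying changes this little.

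**Step 5: finite estimates are also imprecise.** With 1 against 1 event the approximate limits are exp(±1.96·√2) = 0.06 to 16; with 3 against 3, exp(±1.96·√(2/3)) = 0.2 to 5.

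**The case against.** The strongest objection is that the SAP gives no event rates. A reader might infer that several of these hazard ratios are bound to be infinite. The document does not support that. Patients have moderate to severe hepatic impairment (Section 3.1) and continue beyond 48 weeks until database lock, at approximately 3 years (Section 3), so higher risks cannot be ruled out. Taking seven endpoints with a common risk and treating them as independent, two or more lack a finite hazard ratio with probability 98% at 4% risk, 51% at 8% and 10% at 12%. Even these are rough, because the endpoints overlap: liver-related death lies inside all-cause death. A failed estimate can also be zero or absent rather than infinite. This objection stands.

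A reader might also infer that the planned analysis would conceal a one-sided result or report a false one. It would not. For each endpoint, Section 9.6 also calls for event and censoring counts, Kaplan-Meier tables and curves by arm, and a log-rank test, which can still be computed at 0 against 3. Many of the same events are adverse events of special interest (Section 10.3.3), and treatment-emergent events are tabulated by arm (Section 10.3.4). An estimate of 10^12 beside a zero count is visibly degenerate and would not be taken for a real effect. Nor does the SAP prescribe Wald limits; profile-likelihood limits are compatible with its wording.

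Finally, clinical events are exploratory objectives (Section 2.1.3), no formal hypothesis is tested (Section 2.2), and Section 1 requires departures from the SAP to be documented in the study report. This limits the weight of the point. It does not remove the gap: the specified method has a foreseeable failure at this sample size, and the plan does not say what is reported when it occurs.

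**Conclusion.** The point holds as a minor weakness of specification. Section 9.6 applies an ordinary stratified Cox model to each single event and HCC with about 25 patients per arm, and says nothing about sparse events. For a component with a risk of 5% or less per arm, the chance of no finite hazard ratio is about one half or more; at 10% it is 14%, and at 20% it is negligible. These figures rest on equal risk in both arms and on risks that the SAP does not supply. The split by total number of events (49%, 24% and 11% for 2, 3 and 4 events) needs only equal risk.

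What is lost is a usable estimate and interval for rare components, not the visibility of the imbalance. The composite is much less exposed because it pools the listed events. No primary conclusion depends on a component hazard ratio.

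**What to change.** In Section 9.6, before database lock:

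- Estimate the single-event and HCC hazard ratios with the stratified Cox model using Firth's penalty and profile-likelihood 95% CIs (in SAS PROC PHREG, the options FIRTH and RISKLIMITS=PL).
- Print the number of events by arm beside each hazard ratio.
- Show no hazard ratio when neither arm has an event.
- Omit the Schoenfeld check for components with fewer than 5 events in total.
- Leave the composite analysis as planned.

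The hazard ratio should not be dropped altogether below 5 events, because that is where the penalty is most useful.

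The cost is a few sentences of SAP text and two program options. The downside is slight shrinkage of the hazard ratios toward 1. Intervals will remain very wide (0.7 to about 980 in the 0 against 3 example), so the gain is a finite estimate and a usable lower limit, not precision.

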## 3. SUMMARY OF STUDY DESIGN

This is a double-blind, randomized, placebo-controlled study evaluating the PK and safety of OCA in patients with PBC and moderate to severe hepatic impairment. It is a Phase 4 study in regions where OCA has received regulatory approval for PBC; in all other regions, this study is considered Phase 3b.

[figure not shown]
Approximately 50 patients (including at least 20% of patients with CP-C) will be enrolled in the study. Patients will be screened  $\geq 14$  days but not more than 28 days prior to entering the study (Day 1). Patients who meet all eligibility requirements will be randomized in a 1:1 ratio to 1 of 2 treatment groups: placebo or OCA. Randomization will be stratified by CP class. Baseline MELD scores will be monitored on an ongoing basis to ensure adequate distribution of MELD scores.

Patients will receive double-blind treatment for at least 48 weeks. During the 48-week treatment period (ie, Day 1 through Week 48), an initial safety visit will occur at Week 3. After the Week 6 Visit, subsequent clinic visits will occur approximately every 6 weeks for the assessment of safety, tolerability, PK, and PD. Titration may be considered as early as the Week 12 Visit. Fasting PK samples (ie, trough only) will be obtained from all patients on Day 1, Week 6, and Week 36 prior to dose administration. Post-dose serial PK assessments (including a trough sample) will be performed in all patients at Weeks 12, 18, 24, 30, and 48.

Patients who have completed their 48-week double-blind treatment period will continue double-blind treatment until all randomized patients have completed their participation in the 48-week treatment period and the database for that period is locked (approximately 3 years).

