## 5. SUBJECT DISPOSITION

Subject disposition will be tabulated by treatment group and overall and will include the number and proportion of subjects:

- Enrolled
- Randomized
- Randomized but not treated
- ITT Population
- Safety Population
- PK Population
- Non-COVID-19 Impacted Population
- Subjects who completed the study, withdrew from the study and the reasons for the withdrawal
- Subjects who completed the study treatment, withdrew from the study treatment and reasons for the withdrawal
- Subjects who completed Week 48 Visit of double-blind (DB) phase
- Subjects' study status post study treatment as recorded on the eCRF.

Proportions will be out of the number of randomized subjects.

Similar disposition summary will be done also other ITT, Safety, PK and Non-COVID-19 impacted population. Proportions will be out of the number of subjects in the given population.

Subjects' completion/discontinuation status will be listed including subject identifier, informed consent date, treatment completion, date of last treatment, dose regimen at date of last treatment, reason for treatment discontinuation, study completion, date of study completion or early withdrawal, and reason for study discontinuation.

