### 9.1. MELD Score

MELD score is derived from the patient's serum total bilirubin, serum creatinine, and INR, as appropriate, to predict survival ([Kamath 2007](#)). MELD score will be calculated and reported for visits where these parameters are measured as described in the protocol. An increasing MELD score is associated with increased severity of hepatic dysfunction and increased 3-month mortality risk.

- Summary statistics of MELD score including baseline values, change from baseline, and Percentage change from baseline values will be presented by treatment group and by each scheduled post-baseline visit.
- Analysis of change from baseline in MELD score will be analyzed using the Wilcoxon Rank Sum Test. The tabulation will include median, interquartile range for each treatment group, median differences and 95% CI of the median differences between treatment groups using the Hodges-Lehmann estimate. If the median differences between treatments are not symmetrical around the median, the Sign Test may be used.
- MELD score will be presented in shift tables showing the shift from baseline to each scheduled post-baseline visit by the count and percentage of patients within each shift classification (<10, 10 to <12, 12 to <13, 13 to <14, 14 to <15, and  $\geq 15$ ).

The MELD Score analyses will be repeated for MELD-Na

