### 10.3.5. Pruritus Adverse Events

Pruritus: Treatment-emergent pruritus, defined as any PT including “Prur” will be summarized separately by the treatment group, SOC, and PT as a subset of all TEAEs. This summary will be repeated for subjects with “new or worsened” pruritus events, as defined as follows:

- Mild, moderate, or severe treatment-emergent pruritus events in patients with no pruritus at baseline, or
- Worsening of the severity of the baseline condition in patients with pruritus at baseline.

Baseline pruritus is defined as the Investigator’s rating of severity as collected on the PBC Disease History eCRF. Patients whose baseline severity is severe will be counted as worsening if an AE of pruritus with severe is recorded.

An analysis of treatment-emergent pruritus event days per patient years on study will be performed. The days at each severity grade, including the total days of event, the total patient years on study, and the event days per patient year on study at each severity grade, including the total, will be summarized.

In order to explore the relationship between pruritus and the IP, the following time-to-event analyses will be performed:

- Time to first onset of treatment-emergent pruritus

The time to the start of the first episode = date of onset of first episode – date of first dose of IP + 1.

Patients who never reported an AE of pruritus will be censored at the date of last contact.

- Time to onset of the first moderate or severe treatment-emergent pruritus

The time to the start of the first moderate or severe pruritus = date of onset of the first moderate or severe pruritus – date of first dose of IP +1.

Patients who never reported a moderate or severe AE of pruritus will be censored at the date of completion or discontinuation.

- Time to onset of the first severe treatment-emergent pruritus

The time to the start of the first severe pruritus = date of onset of the first severe pruritus – date of first dose of IP +1.

Patients who never reported a severe AE of pruritus will be censored at the date of completion or discontinuation.

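### Time to MELD ≥15 is censored at last contact, although MELD is known only at laboratory visits; event-free subjects should be censored at their last evaluable MELD

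*SAP*

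**What the plan says.** Section 9.6 lists "Time from first dose to MELD score" ≥15, for patients with baseline MELD ≤12, among the clinical outcome events. It enters the composite. It is also analysed on its own, because the section applies its Kaplan-Meier, stratified log-rank and stratified Cox methods to "the incidence and time to each of the above clinical events". For all of these, "subjects who do not experience an event will be censored at the time of their last contact". MELD has no exception, and last contact is not defined.

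Section 9.1 states when MELD can be known: "MELD score will be calculated and reported for visits where these parameters are measured as described in the protocol". In the 48-week period there are visits at Weeks 3 and 6, after which "subsequent clinic visits will occur approximately every 6 weeks for the assessment of safety, tolerability, PK, and PD" (Section 3).

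Two places suggest that last contact and the last laboratory visit can differ. Section 5 tabulates withdrawal from treatment separately from withdrawal from study, and adds "Subjects' study status post study treatment as recorded on the eCRF". Section 10.3.5 says of the first pruritus endpoint "Patients who never reported an AE of pruritus will be censored at the date of last contact", but censors the next two at completion or discontinuation.

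**The concern.** A contact can reveal a death or a transplant. It cannot reveal a MELD of 15 or more, which needs a blood draw. A subject who no longer has laboratory visits but is still contacted stays in the MELD risk set as event-free, with no chance of an event being recorded. That enlarges the denominators without enlarging the event count, so the estimated hazard and event probability fall. If laboratory visits stop more often in one arm, that arm looks better than it is.

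Nothing else in the SAP corrects this. The adjudication requirement in Section 9.6 governs which events count, not time at risk. The rule that treats subjects with no data after randomization as having an event on Day 1 concerns different patients. The missing-data text in Appendix A sets no event-specific censoring date.

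**Working it through.** The SAP gives no event rate, event count or power for this endpoint, so there is no figure of its own to reproduce. The rule was simulated instead.

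**Inputs from the SAP.** Visits at Weeks 3, 6, 12, 18, …, 48 (Section 3); MELD known only at visits (Section 9.1); about 50 patients randomized 1:1 (Section 3.3).

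**Assumptions.** True 48-week probability 0.30, with exponential event times. Laboratory visits stop at random, independently of prognosis, in 15%, 30% or 45% of patients by Week 48. Contact continues for 0, 4.3 (about 30 days), 12 or 24 weeks after the last MELD, or to Week 48. The 15% is borrowed from Section 3.3 ("assuming a 15% discontinuation rate"), where it is a PK sample-size assumption and not a rate of stopping laboratory tests. Each scenario used 400,000 patients.

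**Week 48 Kaplan-Meier probability, censoring at last contact:**

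| Stop testing | No gap | 4.3 weeks | 12 weeks | 24 weeks | To Week 48 |
|---|---|---|---|---|---|
| 15% | 0.299 | 0.299 | 0.290 | 0.283 | 0.276 |
| 30% | 0.301 | 0.299 | 0.279 | 0.263 | 0.250 |
| 45% | 0.301 | 0.299 | 0.267 | 0.241 | 0.221 |

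Censoring the same data at the last MELD returned 0.299 to 0.301 in every cell. With no gap the two rules coincide.

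**Closed-form check of the last column.** If everyone is contacted to Week 48, the Kaplan-Meier estimate is simply the proportion with an observed event. In continuous time, with a = −ln(0.70) = 0.357 and b = −ln(1 − s) for stopping fraction s, that proportion is a/(a + b) × [1 − 0.70 × (1 − s)].

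- s = 0.15: 0.357/0.519 × 0.405 = 0.278
- s = 0.30: 0.5 × 0.51 = 0.255
- s = 0.45: 0.357/0.955 × 0.615 = 0.230

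The simulated values are slightly lower because an event is also lost if testing stops before the next visit.

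**Why short gaps hardly matter.** Events are dated at visits. A subject last tested at Week 12 and contacted to Week 16.3 has left the risk set before the next event time, Week 18.

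**Other true probabilities.** With contact to Week 48, a true 0.20 becomes 0.184 (15% stopping) or 0.166 (30%). A true 0.40 becomes 0.368 or 0.335.

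**Hazard ratio (true value 1.0, probability 0.30), censoring at last contact:**

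| Stop testing, OCA / placebo | 4.3 weeks | 12 weeks | To Week 48 |
|---|---|---|---|
| 15% / 15% | 1.00 | 1.00 | 1.00 |
| 30% / 15% | 0.99 | 0.97 | 0.90 |
| 45% / 15% | 0.99 | 0.91 | 0.79 |

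Under last-MELD censoring these nine scenarios gave 0.99 to 1.01, which shows the simulation noise.

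**Against sampling error.** Take 25 per arm, an upper limit because of the MELD ≤12 restriction. The standard error at 0.30 is √(0.30 × 0.70/25) = 0.092, so the 95% half-width is 1.96 × 0.092 = 0.18. With 0.30 × 25 = 7.5 events per arm, the standard error of the log hazard ratio is √(2/7.5) = 0.516, and a hazard ratio of 1 has an interval of about 0.36 to 2.75.

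**The case against.** The strongest reply is that the gap is assumed. Whether laboratory visits stop while contact continues depends on the protocol's visit schedule and off-treatment follow-up, which are not at hand. Parts of the SAP point the other way:

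- Appendix A keeps baseline values unchanged if a subject stops IP and starts commercial OCA. That rule is needed only if later values are still collected.
- Separate recording of treatment and study withdrawal fits patients who stop IP but stay in scheduled visits.
- Section 10.3.4 equates the last recorded study visit with the end-of-study date.
- Section 10.3.6 uses last contact for all three fatigue endpoints, so the mixed dates for pruritus may be loose wording.

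This stands as a limit on size. The gap is possible under Section 5 but not quantified anywhere. It does not rescue the rule, which is sound for this endpoint only if contact never meaningfully outlasts testing.

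A reader might infer that the rule could hide hepatic worsening on OCA. The SAP does not support going that far. The endpoint is exploratory (Section 2.1.3), there is no formal hypothesis (Section 2.2), and the plausible shifts are small beside the sampling error. MELD is also summarised by visit, with shift tables that include a ≥15 category and a Wilcoxon analysis (Section 9.1). A persistent 3-point rise is an adverse event of special interest (Section 10.3.3). None of these uses the censoring rule.

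A reader might also infer that the composite should be censored when all components were last assessed. That could discard later deaths, transplants and hospitalizations, a worse loss in Child-Pugh B and C patients than the bias it would remove.

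**Conclusion.** The point holds as a defect in one censoring rule for one exploratory component. Where contact outlasts MELD testing, the Kaplan-Meier probability of MELD ≥15 is biased down; no simulated scenario with a gap of 12 weeks or more moved it up. The bias is nil without a gap and negligible below about one visit interval. At an assumed true 48-week probability of 0.30, it is about 0 to 2.5 points if 15% stop testing and up to 5 points if 30% do. The hazard ratio is essentially unaffected if stopping is equal in both arms. With 30% stopping on OCA and 15% on placebo, a true 1.0 becomes about 0.97 (12-week gap) to 0.90 (contact to Week 48).

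The event probability, the gap lengths and the use of these stopping fractions for laboratory visits are assumptions, and the calculation covers only the 48-week period. No primary conclusion is at risk. The change is worth making because the rule does not fit how the event is observed and the correction is cheap.

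**What to change.** In Section 9.6:

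- For time to MELD ≥15, censor event-free subjects at the date of their last evaluable MELD assessment.
- Censor on Day 1 those with some post-randomization data but no post-baseline MELD. State explicitly how this sits beside the existing rule that counts subjects with no data after randomization as having an event on Day 1, so that no subject falls under both.
- Define last contact, and keep it as the censoring date for death and transplant.
- Leave the composite's main analysis as it is, counting all later deaths, transplants and hospitalizations. Add a sensitivity analysis that censors event-free subjects at their last MELD assessment. Because later hard events still count while event-free time is cut, that analysis leans upward and should be read beside the main one, not in place of it.

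The cost is a few sentences, one derived date and one extra table. Nominal follow-up for this component becomes slightly shorter. Last-MELD censoring does not cure informative dropout: if worsening patients stop visits, it is biased too. It recovered the true probability here only because stopping was simulated as independent of prognosis.
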